#### 5-1.2 Specific Aim/Hypothesis

We are interested in determining if and how tDCS can be used as a tool to improve language ability in aphasic patients when used in conjunction with language therapy. We would like to assess the patient-specific parameters under which tDCS is effective: specifically, whether factors like lesion size and location, aphasia severity and type, and time post-stroke influence the efficacy of tDCS with language therapy.

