#### 5-1.5 Methodology

Subjects will be recruited from the University of Michigan Aphasia Program. In this clinical program, clients undergo intensive language therapy over four weeks which includes a combination of individual therapy (about 14 hours a week), group therapy (about 6 hours a week), and computer-based therapy (about 5 hours a week). This project will consist of tDCS sessions administered during the course of this clinical care. Subjects will receive up to 30 sessions of active tDCS over the left hemisphere while undergoing individual behavioral therapy. The standard numeric analogue scale used for pain in UMHS with the addition of faces on a scale of 1 to 10 will be placed in front of the client to allow them to communicate any discomfort they may feel and if they would like to stop the study.

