#### 5-1.6 Statistical Design

We will compare the baseline performance of subjects to their performance after tDCS in conjunction with language therapy, including specific measures of word fluency and naming. We have data collected from a group of 300 subjects who received the same type of therapy without tDCS which we can use as a “control group” to compare the effect of therapy alone to the effect of therapy with tDCS. We will also assess subject parameters as they relate to their performance, including age, time post-stroke, type and severity of aphasia, location and size of lesion, and other relevant variables. If possible, we will also have follow-up meetings with the subjects either 4 weeks post-therapy or 8 weeks post-therapy to see how long improvement is maintained.

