### **tDCS**

Parameters: All subjects will receive up to 30 sessions of active tDCS. Depending on the availability of the subject, the session number may vary from 15 to 30 sessions. Each session will begin with up to 20 minutes of active tDCS at 2mA in conjunction with the individual behavioral therapy. The anode electrode will be placed over the left hemisphere and the reference electrode will be placed on the contralateral frontopolar cortex. The specific montage will be determined based on individual patient characteristics.

Risks: tDCS is generally considered safe with no more than minimum risk. In a meta-analysis of over 200 tDCS studies conducted from 1998 to 2010, 56% of studies mentioned adverse events (Brunoni et al., 2011). The available evidence suggests that it is safe. However, it is investigational in nature, which means that we are doing these studies to learn more about tDCS. The most common side effects associated with tDCS based on the available scientific data are:

Sensations under the electrode: These sensations usually stop shortly after tDCS begins but can sometimes continue throughout and for a brief period after tDCS.

- Mild tingling • Light itching • Slight burning sensation • Discomfort

Effects reported that occur ONLY during tDCS:

- Visual sensation during switching on and off the stimulation

Other effects that can occur both during and after tDCS include:

- Fatigue,
- Skin redness
- Headache
- Changes in concentration, memory, or other cognitive abilities. This is partially what we will be testing.

Additionally the following rare side effects have been described in previous studies that used tDCS:

- Nausea
- Nervousness
- It is also possible that the electric current can cause a burn on your skin. This is unlikely because we are using a smaller dose than what is known to cause burns and because we use saline or gel to reduce electrical resistance that leads to burns.
- A shock-like sensation at the initiation of tDCS was reported in one participant.
- Changes in the activity of the prefrontal region (front of the head) have the potential to induce sudden changes in your mood. Hypomania has been reported in a few patients receiving tDCS for bipolar disorder and depression but never in normal controls.

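### The aim asks which patient factors make tDCS effective, but the stated analysis specifies no factor-by-group contrast with the therapy-only subjects

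*Combined protocol and SAP*

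**What the plan says.** All references are to the combined protocol and SAP.

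- **Aim (5-1.2).** "We would like to assess the patient-specific parameters under which tDCS is effective". After a colon, the sentence narrows this to whether lesion size, lesion location, severity and type of aphasia, and "time post-stroke influence the efficacy of tDCS with language therapy".
- **Overall comparison (5-1.6).** Subjects are compared with their own baseline, "including specific measures of word fluency and naming". Existing data on 300 people who had the same type of therapy without stimulation can serve as a control group "to compare the effect of therapy alone to the effect of therapy with tDCS".
- **Factor analysis (5-1.6).** The next sentence is "We will also assess subject parameters as they relate to their performance, including age, time post-stroke, type and severity of aphasia", followed by lesion location and size and other variables. No model, interaction, subgroup-specific group difference or other comparison of these associations between the two groups is given.
- **Treatment (tDCS, Parameters).** "All subjects will receive up to 30 sessions of active tDCS", and "the session number may vary from 15 to 30 sessions" according to availability. The electrode montage is chosen for the individual patient. Section 5-1.5 places stimulation within the individual therapy of a four-week intensive programme.

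**The concern.** The first part of the aim is a question about effect modification: for which patients does stimulation add something? All enrolled subjects are stimulated and all have intensive therapy, so how they fare without stimulation can only be learned from the 300. Section 5-1.6 brings those 300 in for the overall comparison but does not say that they enter the factor analysis through a contrast.

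Two errors could follow. A factor that predicts gain from therapy alone could be reported as a condition under which tDCS works. A factor that truly modifies the tDCS effect could go unseen because its prognostic effect runs the other way. More tDCS subjects analysed in the same way would not help, because the quantity estimated stays the same.

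**Working it through.** **1. Inputs.** From the documents: 300 therapy-only subjects (5-1.6), all enrolled subjects on active tDCS (tDCS section), five factors in the aim (5-1.2) and two named outcome areas (5-1.6). The documents give no tDCS sample size, SD, effect size, alpha or power, so there is no planned figure to reproduce. Everything numerical below is an assumption, used to show how the estimates behave.

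**2. Algebra.** Let *b* be the slope of gain on a factor under therapy alone, *g* the change in that slope due to tDCS, *n* the tDCS subjects and *m* the controls.

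- Slope within tDCS subjects: *b + g*.
- Slope within controls: *b*, if the groups are comparable.
- Difference between them (factor-by-group interaction): *(b + g) − b = g*.
- Slope in pooled data with a group term but no interaction, same spread of the factor in both groups: *b + g·n/(n + m)*.

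Only the third line targets *g*, and only if the groups are comparable. The first line does so only when *b* = 0.

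**3. Three illustrative cases (SD units).**

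| *b* | *g* | Within tDCS | Interaction |
|---|---|---|---|
| 0.5 | 0 | 0.5 | 0 |
| 0 | 0.5 | 0.5 | 0.5 |
| 0.5 | −0.5 | 0 | −0.5 |

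The first two cases look identical within tDCS subjects. In the pooled slope, *g* gets a weight of 20/320 = 0.06 for an assumed 20 tDCS subjects, or 40/340 = 0.12 for 40. The slope is then almost entirely prognosis.

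**4. Simulation.** 2,000 replicates per case, residual SD 1, two-sided alpha 0.05, 300 controls, no confounding between groups.

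| tDCS *n* | *b* = 0.4, *g* = 0: tDCS-only significant | same: interaction significant | *b* = −0.4, *g* = 0.4: tDCS-only significant | same: interaction significant |
|---|---|---|---|---|
| 20 | 36% | 5% | 5% | 37% |
| 40 | 66% | 5% | 4% | 63% |
| 60 | 85% | 5% | 5% | 80% |
| 100 | 97% | 5% | 5% | 92% |

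A purely prognostic factor is flagged more often as *n* grows. A modifier offset by prognosis stays at the nominal error rate at every *n*.

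**5. Price in precision.** For a 50/50 factor, residual SD 1, the 95% half-width is 1.96 × 2 × √(1/n + 1/m).

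- Interaction, m = 300: 3.92 × √(1/20 + 1/300) = 0.91 SD at n = 20, and 0.66 SD at n = 40.
- Interaction, if only 50 controls were usable: 1.04 and 0.83 SD.
- tDCS subjects alone: 3.92 × √(1/20) = 0.88 SD, and 0.62 SD at n = 40.
- Continuous factor, per SD, m = 300: half the first line, 0.45 and 0.33 SD.

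With most of the 300 usable, the right contrast costs little precision over the tDCS-only slope. Both are imprecise because the tDCS group is assumed small.

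**The case against.** **The aim may concern the combined treatment.** The narrowing clause in 5-1.2 speaks of efficacy with language therapy, and the sentence before it also pairs the two. On that reading, predicting response to the package is close to what is wanted. This stands in part: the text is ambiguous. But the opening clause names tDCS by itself, and the Background (5-1.3) asks when tDCS is a useful tool and whether stimulation improves outcomes of traditional therapy. If the package is meant, the plan should say so.

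**The word *their* may include the 300.** A reader might infer that the plan confines the factor analysis to tDCS subjects. The documents do not support that. The sentence follows directly on the one about the 300 and the wording is loose. What can be said is that no between-group contrast is specified, and that pooling without one does not isolate modification.

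**The interaction is no clean answer.** A reader might infer that it would separate prognosis from modification. It would do so only under comparability that nobody can assure: controls are not randomised, tDCS subjects are selected by referral, consent and exclusions, montage depends on the patient, and session number varies. The documents do not say whether lesion data exist for the 300. All of this stands and limits what the fix can deliver.

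**The question is exploratory and the harm conditional.** True. The plan does not commit to a claim about modifiers, so the harm depends on how results are later labelled. That is a reason for modest severity and for fixing the labels now.

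**Conclusion.** The concern holds as a gap between the aim and the stated analysis. Without a factor-by-group contrast, associations from section 5-1.6 can support statements about who responds to tDCS plus therapy, but not about the conditions under which tDCS is effective. This follows from the design and the algebra and does not depend on the assumed numbers.

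Its size for this trial cannot be estimated. Reading the tDCS-only slope as modification is wrong by exactly the prognostic effect *b*, which the documents do not give. The programme totals (14 + 6 + 5) × 4 = 100 hours of therapy, against 5 to 10 hours of stimulation at most (15 to 30 sessions of up to 20 minutes, given during that therapy). A reader might infer from this that prognosis must dominate, but hours do not measure how strongly a factor predicts gain. Nor do the documents show that the data cannot answer the question: that depends on what was recorded for the 300.

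It should be fixed, with medium confidence, given the ambiguity in the aim.

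**What to change.** Replace the factor sentence in section 5-1.6 with text such as:

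> For each of lesion size, lesion location, aphasia severity, aphasia type and time since stroke that is recorded in the therapy-only subjects, and for naming and word fluency where measured in the same way in both groups, we will fit a baseline-adjusted model to both groups and report the factor-by-group interaction with a 95% CI. These analyses are exploratory, because the controls are not randomised and montage and session number vary with the patient. Factors not recorded in the controls will be reported as predictors of response to the combined treatment, not of tDCS efficacy.

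State how many controls have each factor and outcome.

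**Cost.** A change of wording, a check of the control data, and up to 5 × 2 = 10 models on data the sponsor already holds.

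**Downsides.** Intervals will probably be wide, and wider still for factors with several levels such as aphasia type or lesion location, so few firm claims about modifiers should be expected. Residual confounding remains, and the interaction absorbs any link between a factor and montage or session number. For factors missing in the controls, possibly the lesion measures, the change is relabelling only.

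### The severity analysis in 5-1.6 can show an association with performance when tDCS has no effect, because performance is undefined, severity is not kept apart from the outcome tests, and the therapy-only group is not used

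*Combined protocol and SAP*

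**What the plan says.** The aim in 5-1.2 is one of effect modification: "whether factors like lesion size and location, aphasia severity and type, and time post-stroke influence the efficacy of tDCS". Severity is one of five factors listed there (lesion size, lesion location, severity, type, time post-stroke).

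The only analysis offered for that aim is one sentence in 5-1.6: "We will also assess subject parameters as they relate to their performance, including age, time post-stroke, type and severity of aphasia". The main comparison in the same section is before against after: "We will compare the baseline performance of subjects to their performance after tDCS". The only measures named are word fluency and naming, and the list is open-ended. No severity instrument, time of severity measurement, form of the outcome or statistical model is given.

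Under the tDCS heading, "All subjects will receive up to 30 sessions of active tDCS"; there is no concurrent group without stimulation. Section 5-1.6 does mention an outside group: "We have data collected from a group of 300 subjects who received the same type of therapy without tDCS". Its stated use is "to compare the effect of therapy alone to the effect of therapy with tDCS", which is the overall effect. The sentence on subject parameters does not refer to it.

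**The concern.** Severity of aphasia and a naming or fluency score describe closely related abilities. Relating one to the other among treated subjects can produce an association by two routes that have nothing to do with tDCS.

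- **After-score.** Subjects who are worse at baseline tend to be worse afterwards. This is prognosis. It does not depend on measurement error or on whether severity and outcome share a test.
- **Change.** If severity is read from the outcome test's own baseline score, the error in that score enters severity and, with opposite sign, the change. A subject who scores low by chance looks both severe and improved.

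The two routes point in opposite directions. With an identical gain in everyone, the study could report that mild patients do best (after-score) or that severe patients benefit most (change). Which one is reported would depend on a choice the plan leaves open and that could be made after the data are seen. The answer to a named aim is at stake. The overall comparison of therapy with and without tDCS is not affected by this point.

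**Working it through.** The documents give no sample size, significance level, SD or reliability, so there is no stated figure to reproduce. The check asks what the analysis in 5-1.6 would show if tDCS did nothing and everyone gained the same amount from therapy.

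**Inputs**
- From the documents: all subjects treated; 300 therapy-only subjects; naming and word fluency among the outcomes.
- Assumed: test-retest reliability r = 0.7 to 0.9; n = 30 or 50 (20 to 100 in some runs); two-sided 5% test of a correlation; normal scores. A higher score means better language, so a negative correlation of baseline with change means that severe subjects appear to gain more.

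**1. Performance = after-score.** With equal SDs, the correlation of the baseline score on the same test with the after-score is r, that is 0.7 to 0.9. In simulation it is significant in over 99% of null trials at n=30. With a separate severity test of the same ability the figure is still over 99%.

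**2. Performance = change, severity = baseline score on the same test.** Let k = SD(after)/SD(baseline). Then

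corr(baseline, change) = (rk − 1) / √(1 + k² − 2rk), which is −√((1 − r)/2) at k = 1.

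| r | −√((1 − r)/2) | null trials significant, n=30 | n=50 |
|---|---|---|---|
| 0.9 | −√0.05 = −0.22 | 22% | 35% |
| 0.8 | −√0.10 = −0.32 | 41% | 62% |
| 0.7 | −√0.15 = −0.39 | 57% | 81% |

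Repeated simulations agree to within about one percentage point. The result depends on k. The correlation is zero at k = 1/r (1.25 for r = 0.8; 1.11 for r = 0.9) and positive above that.

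**3. Performance = change, severity = mean of m tests, one of them the outcome test.** With equal weights, one underlying ability and independent errors,

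corr = −[(1 − r)/m] / √{[r + (1 − r)/m] · 2(1 − r)}.

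For r = 0.8 and m = 2: −0.10/√(0.90 × 0.40) = −0.17. For m = 5: −0.04/√(0.84 × 0.40) = −0.07. Significant null trials at n=30:

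| r | m=1 | m=2 | m=3 | m=5 |
|---|---|---|---|---|
| 0.9 | 22% | 9% | 7% | 5–6% |
| 0.8 | 41% | 14% | 9% | 6% |
| 0.7 | 57% | 20% | 12% | 7–8% |

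**4. Performance = change, severity from a separate test with independent error.** About 5%: no artefact.

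**5. Severity-by-group interaction on change, tDCS subjects against the 300.** Even with severity taken from the outcome's own baseline, the rate was 4.2% to 5.6% for n = 20 to 100 and r = 0.8 or 0.9, because the same artefact sits in both groups and cancels. This assumes comparable groups. The slope of change on baseline at k = 1 is r − 1, so if reliability were 0.8 in one group and 0.9 in the other, the slopes would be −0.20 and −0.10 and the cancellation would be incomplete.

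**The case against.** A reader might infer that severity is measured by the outcome tests themselves, so that any reading of performance yields a spurious result. The documents do not support that. No severity instrument is named, and naming and fluency are given as examples, so other outcomes may exist. Overlap is plausible but not shown. With change as the outcome and a separate severity test, the null rate is the nominal 5%. With a composite severity score the inflation runs from moderate to negligible. The 22% to 57% range belongs to the extreme case in which severity is the outcome's own baseline score. This objection stands and limits the claim.

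It can also be said that the after-score association is prognosis and not measurement error. That is correct: it grows as reliability rises, and a separate severity test does not remove it.

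A third argument is that re-scoring severity alone does not answer the aim in 5-1.2. Therapy runs at about 14 + 6 + 5 = 25 hours a week, and response to it may itself vary with severity. Inside a fully treated group that cannot be told apart from modification of the tDCS effect. This stands too, and is why the comparison with the therapy-only group belongs in the fix.

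The argument that this is only missing detail does not stand. The analysis in the text, applied to treated subjects alone, can give a wrong answer to a stated aim in either direction.

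**Conclusion.** The point holds in a limited form. As written, the severity analysis cannot show whether severity influences the efficacy of tDCS, and it can produce an association when tDCS does nothing. On the after-score reading the association is near certain (over 99% of null trials at n=30). On the change reading it depends on how severity is measured: about 22%, 41% or 57% at n=30 for reliability 0.9, 0.8 or 0.7 if severity is the outcome's own baseline; about 14% and 6% for composites of two and five tests at reliability 0.8; and 5% for a separate test.

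Sample size, reliability, a uniform gain and equal SDs at the two times are assumptions. The direction and size of the change artefact depend on the SD ratio. What rests on the documents alone is that performance is undefined, severity is not separated from the outcome, all subjects are treated, and the therapy-only group is not tied to this analysis. The change should be made, since a named aim depends on it.

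**What to change.** In 5-1.6:

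1. Name the severity instrument and state that it is scored at baseline. State that the dependent variable in the severity analysis is change on the named outcome test.
2. Score severity from baseline tests other than that outcome where they are available, for example by leaving out any naming or fluency parts.
3. Test severity as a severity-by-group interaction between the tDCS subjects and the 300 therapy-only subjects, with severity and outcome measured the same way in both groups.
4. State that a correlation of severity with after-score or with change inside the tDCS group alone will not be reported as evidence that severity influences tDCS efficacy.

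The cost is mainly wording, plus re-scoring if the severity measure has separable parts. A severity score without the outcome subtests is slightly less reliable. The interaction is a non-randomised comparison, so differences between the groups could still bias it. It also needs the historical subjects to have the same measures, which the documents do not state. If they do not, the plan should say that the severity question cannot be answered for tDCS specifically.

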### **Participants**

Recruitment: Clients who are participating in the University of Michigan Aphasia Program and meet study criteria will be invited to join this study. Clients who are identified by the [name] as a potential subject, will first be asked if they would like to hear about the study from a member of the research team. If the patient consents, then the member of the research team will meet with the patient and a family member if present to discuss the study. Only subjects with aphasia will participate in this study.

Inclusion criteria: Chronic receptive or expressive aphasia with or without apraxia.

Exclusion criteria: Any implanted devices or surgical instruments, history of severe mental illness or epilepsy, no active history of seizures (within three months). As the risks to pregnancy, are unknown, no pregnancy or plan to become pregnant during the study period will also be an exclusion criteria.

### **tDCS**

Parameters: All subjects will receive up to 30 sessions of active tDCS. Depending on the availability of the subject, the session number may vary from 15 to 30 sessions. Each session will begin with up to 20 minutes of active tDCS at 2mA in conjunction with the individual behavioral therapy. The anode electrode will be placed over the left hemisphere and the reference electrode will be placed on the contralateral frontopolar cortex. The specific montage will be determined based on individual patient characteristics.

Risks: tDCS is generally considered safe with no more than minimum risk. In a meta-analysis of over 200 tDCS studies conducted from 1998 to 2010, 56% of studies mentioned adverse events (Brunoni et al., 2011). The available evidence suggests that it is safe. However, it is investigational in nature, which means that we are doing these studies to learn more about tDCS. The most common side effects associated with tDCS based on the available scientific data are:

Sensations under the electrode: These sensations usually stop shortly after tDCS begins but can sometimes continue throughout and for a brief period after tDCS.

- Mild tingling • Light itching • Slight burning sensation • Discomfort

Effects reported that occur ONLY during tDCS:

- Visual sensation during switching on and off the stimulation

Other effects that can occur both during and after tDCS include:

- Fatigue,
- Skin redness
- Headache
- Changes in concentration, memory, or other cognitive abilities. This is partially what we will be testing.

Additionally the following rare side effects have been described in previous studies that used tDCS:

- Nausea
- Nervousness
- It is also possible that the electric current can cause a burn on your skin. This is unlikely because we are using a smaller dose than what is known to cause burns and because we use saline or gel to reduce electrical resistance that leads to burns.
- A shock-like sensation at the initiation of tDCS was reported in one participant.
- Changes in the activity of the prefrontal region (front of the head) have the potential to induce sudden changes in your mood. Hypomania has been reported in a few patients receiving tDCS for bipolar disorder and depression but never in normal controls.

Subjects with a history of bipolar disorder will be excluded from the study. At this time, tDCS has never been reported to cause a seizure in any patient population. Seizures are, however, theoretically possible and a seizure plan is in place for such an unlikely event. Importantly, the majority of the above side effects have been also reported in association with sham (fake) tDCS, even with similar rates. The table below comes from a recent review of tDCS safety and shows the percentage of studies reporting these common sensations (Brunoni et al., 2011) These data suggest that other factors may cause these sensations, such as your expectations or the pressure of head straps or caps.

**Table 3.** Frequency of adverse effects in 117 (active group) and 82 (sham group) experiments. We considered the presence of adverse effect if the study reported its occurrence in at least one patient

Sensation	Active group	Sham group
Itching	46 (39.3%)	27 (32.9%)
Tingling	26 (22.2%)	15 (18.3%)
Headache	17 (14.8%)	13 (16.2%)
Burning	10 (8.7%)	8 (10%)
Discomfort	12 (10.4%)	11 (13.4%)
Total	117 studies	82 studies

Due to the investigational study, there may be risks, side effects that are not yet

nature of this discomforts or known.

We will follow current safety guidelines for tDCS and will use a current strength of up to 2mA and a duration of up to 20 minutes. Few, if any, side effects are reported with these parameters (Nitsche & Paulus, 2011). We will also monitor subjects for discomfort during and after each session. During the session, we will verbally ask the subject if they are experiencing discomfort. The Speech-Language Pathologists will be in the room while the stimulation is being applied and will consequently be available to assist the patients in communicating any side effects they may be experiencing. After the sessions, subjects will complete the following post-tDCS questionnaire:

tDCS Adverse Effects Questionnaire – Session \_\_\_\_\_

---

Do you experience any of the following symptoms or side-effects?	Enter a value (1–4) in the space below (1, absent; 2, mild; 3, moderate; 4, severe)	If present: Is this related to tDCS? (1, none; 2, remote; 3, possible; 4, probable; 5, definite)	Notes
Headache			
Neck pain			
Scalp pain			
Tingling			
Itching			
Burning sensation			
Skin redness			
Sleepiness			
Trouble concentrating			
Acute mood change			
Others (specify)			

---

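### With open-label tDCS and comparison subjects who had no device described, even a well-matched contrast estimates adding open-label tDCS to therapy and cannot by itself establish the efficacy of the stimulation

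*Combined protocol and SAP*

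**What the plan says.** Section 5-1.2 Specific Aim/Hypothesis asks whether and how tDCS, given alongside language therapy, improves language in people with aphasia. It also asks which patient features influence its efficacy.

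Section 5-1.5 Methodology sets the treatment: "Subjects will receive up to 30 sessions of active tDCS over the left hemisphere while undergoing individual behavioral therapy". The tDCS section repeats that every subject is treated actively: "All subjects will receive up to 30 sessions of active tDCS". Sham stimulation appears in the document only where side effects in other studies are cited.

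The same section describes monitoring during stimulation: "The Speech-Language Pathologists will be in the room while the stimulation is being applied", and "During the session, we will verbally ask the subject if they are experiencing discomfort". A questionnaire after the sessions asks about symptoms and how far each is related to tDCS.

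Section 5-1.6 Statistical Design plans a before-after comparison, with naming and word fluency among the measures, and an external comparison: "We have data collected from a group of 300 subjects who received the same type of therapy without tDCS". These people are to serve as controls, so that results with therapy by itself can be set against results when stimulation is added. The document does not say who administers or scores the language measures, or whether that person is masked.

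**The concern.** The comparison with the 300 is the only analysis that could separate tDCS from the intensive therapy everyone receives; the before-after change contains both. If that comparison favours the tDCS subjects, 5-1.2 invites the reading that stimulation works. The groups differ in more than current, however. One group has treatment that subject and therapist can be taken to know is active; the other had therapy with no device described. Naming and fluency are performance measures and can respond to a subject's effort and a therapist's encouragement.

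The protocol accepts in another setting that non-specific effects are possible. On side effects it says: "These data suggest that other factors may cause these sensations, such as your expectations or the pressure of head straps or caps". It does not carry that caution over to the language outcomes or to the conclusion that 5-1.6 will support.

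This is separate from case-mix or calendar-time differences between the groups. Those can be partly addressed by matching or adjustment. The present problem cannot, so a team that attended only to matching would leave it in place.

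**Working it through.** The documents give no number of tDCS subjects, significance level, power, effect size or standard deviation, so there is no design figure to reproduce. The check sets the sections side by side.

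**Inputs**

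| Item | tDCS subjects | The 300 | Source |
|---|---|---|---|
| Therapy | Four-week intensive program | Same type | 5-1.5, 5-1.6 |
| Current | Active for all | None | tDCS section, 5-1.6 |
| Sham or masking | None described | No device described | Whole document |
| Therapist during stimulation | Present | Not applicable | tDCS section |
| Device-related contact | Set-up, discomfort question, questionnaire | None described | tDCS section |

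**Step 1. Write out each group's mean change.** Let T be the effect of the therapy program, including the expectation and encouragement that go with it. Let S be the effect of the current. Let E be the additional effect of the subject's knowing that stimulation is given, and A that of the therapist's knowing. Let B be any difference between the groups in case mix or period.

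- tDCS subjects: T + S + E + A + B
- The 300: T
- Difference: S + E + A + B

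**Step 2. Suppose matching is perfect.** Then B = 0 and the difference is S + E + A. Matching acts on B alone.

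**Step 3. Ask whether S can be recovered.** It could if some subjects had E + A without S, as under masked sham, or S without E + A. Every tDCS subject has all three and the 300 have none, so only the sum is estimable.

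**Step 4. Ask whether a larger study helps.** With n tDCS subjects, the standard error of the difference is SD × √(1/300 + 1/n). It falls as n grows; E + A does not. A larger n gives a more precise estimate of the sum and no more information on S.

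**Step 5. Compare with the stated purposes.** The phrase in 5-1.6, "to compare the effect of therapy alone to the effect of therapy with tDCS", can be read as asking for S + E + A, which the design delivers once B is dealt with. Section 5-1.2 asks about the efficacy of tDCS, which is a question about S. Nothing in 5-1.6 limits the conclusion to the sum.

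**The case against.** The strongest reply is that the planned contrast is coherent as written. Therapy with tDCS against therapy alone is a pragmatic add-on question, an unmasked study with an external comparison group is a legitimate early design, and the protocol nowhere says a difference will be called proof. This stands, and it is why the point concerns the conclusion and does not call for a different design.

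Several further points also stand:

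- The 300 were in the same type of program and had expectations and motivated therapists too. Only the increment due to the device enters the difference.
- A therapist would be present in individual therapy anyway. Presence does not distinguish the groups; awareness of the device does.
- The additional attention visible in the document is modest: device set-up, a discomfort question and a questionnaire.
- That subjects and therapists know the stimulation is active is an inference from universal active treatment, no described masking and the therapist's presence. The consent pages are not available to confirm it.
- Comparisons among tDCS subjects, such as by lesion or time since stroke, are less exposed, because an E + A common to all of them cancels.

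Three stronger readings are tempting and are not supported.

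- A reader might take Table 3 as a measure of the bias, for example itching in 46/117 = 39.3% of active against 27/82 = 32.9% of sham experiments. The table counts experiments in which at least one patient was affected, and it concerns sensations, not language. The protocol's remark on expectations is also tentative and offers a physical alternative.
- A reader might infer that treating therapists will score their own clients leniently. The document is silent on who scores; that is a gap to clarify, not evidence of biased scoring.
- A reader might think masked rescoring would cure the problem. It would leave expectation untouched, and if the 300 have no recordings it would make scoring differ between the groups being compared.

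**Conclusion.** The concern holds in this form: even with perfect matching, the comparison with the 300 estimates the effect of adding open-label tDCS to therapy, meaning the current plus any expectation and therapist-awareness effects. It cannot by itself establish the efficacy of tDCS as 5-1.2 intends.

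The size and even the existence of a material non-specific effect cannot be derived from the documents. No figure is offered, because any figure would rest on an assumed bias, sample size and significance level.

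The conclusion rests on two readings of the text: that the absence of any described sham or masking means there is none, and that the 300 had no device. It does not depend on who scores the outcomes. The study can proceed as designed; what needs correcting is what it may claim.

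**What to change.** In 5-1.6 Statistical Design, add two statements:

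1. The comparison with the 300 estimates the effect of adding open-label tDCS to language therapy, including any effects of expectation and therapist awareness.
2. A positive difference will be reported as grounds for a sham-controlled test, and not as evidence that the stimulation itself improves language.

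The cost is a weaker claim. No change to treatment, recruitment or data collection is needed.

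Masked rescoring is not required. If the team chooses to obtain masked scores, they should serve the before-after analysis only. Routine scores should be kept for the comparison with the 300, so that this change does not itself make scoring differ between the groups.
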